RESEARCH PLAN

Effects of telerehabilitation on occupational performance of stroke patients treated by the Occupational Therapy service: a randomized clinical trial.

Principal Investigator: [name]

Associate Researchers: [name], [name], [name], [name]

Department/Institute: Department of Legal Medicine, Bioethics, Occupational Medicine, and Physical Medicine and Rehabilitation / Institute of Physical Medicine and Rehabilitation of the Hospital das Clínicas

CAAE: 86185525.8.0000.0068

Version: 3

Opinion Number: 7.441.169

Location: São Paulo, Brazil

Date of approval: August 21, 2025

RESEARCH PLAN

SUMMARY

Stroke represents a health problem with increasing incidence in the world population. The consequences of the injury are not limited to physical deficits, but also encompass significant biopsychosocial changes. This study aims to evaluate the effect of using telehealth, specifically telerehabilitation, correlated with the practice of Occupational Therapy for the population affected by stroke. To this end, a randomized study will be conducted, which will involve data collection through a structured sociodemographic questionnaire and standardized scales: Scale of Instrumental Activities of Daily Living, Katz Scale, and the Motor Activity Log, which will be applied to the intervention group and the control group. Participants will be users of the Unified Health System (SUS) who are on the waiting list, with an indication for Occupational Therapy services in an outpatient or inpatient setting at the Institute of Physical Medicine and Rehabilitation of the Hospital das Clínicas of the Faculty of Medicine of the University of São Paulo (IMREA FMUSP). The intervention group is expected to show improved occupational performance in response to the guidance provided to patients and caregivers.

Keywords: Stroke (D020521), Digital Public Health (DDCS060401), Telemedicine (D017216), Occupational Therapy (D009788).

INTRODUCTION

A stroke is a significant neurological injury, characterized by an abrupt change in brain function, and is currently the leading cause of disability worldwide (Steinmetz et al., 2024). It can be caused by two distinct pathophysiological mechanisms: ischemic, accounting for 85% of cases, and hemorrhagic, accounting for 15% (Vieira et al., 2020). In 2020, the total costs to the public health system for stroke in Brazil amounted to 416 million Brazilian Reais (BRL) (Reis; Chaoubah, 2024). The estimated incidence of this pathology in the country is 232,000 to 344,000 new cases per year (Ministry of Health, 2021). The sequelae caused by stroke can lead to loss of autonomy and independence for the individual, making it impossible to perform Basic Activities of Daily Living (ADL) and Instrumental Activities of Daily Living (IADL), impacting their family and social interactions, due to the need for assistance, in many cases, to perform various tasks (Vieira et al., 2020; Castro; Martins; Colto; Reis, 2018).

Post-stroke treatment involves a wide range of care and should be intensive, timely, and multidisciplinary (Langhorne; Sandercock; Prasad, 2009). Therefore, efficient treatment has a significant impact on costs, making access to specialized post-stroke treatment services important (Fonseca et al., 2018). Ensuring access to rehabilitation services is fundamental to the recovery process, as it contributes to social reintegration and the resumption of occupational performance (Platz, 2021). However, several barriers impede access, ranging from the organization of health services, due to a lack of material or human resources, to financial resources and the family dynamics of the stroke victim (Santos et al., 2022). In this context,

RESEARCH PLAN

telehealth is a service modality that has been used to address these shortcomings (Luz, 2022; Silva et al., 2023).

The term telehealth is comprehensive, encompassing teleconsultation, telemonitoring, teleconsulting services, telemedicine, telerehabilitation, among others, to provide remote health services through telecommunications and digital information technologies (COFFITO, 2020; Cason, 2012). Telerehabilitation, specifically, is a field of telehealth correlated with the provision of remote rehabilitation services to users, using Information and Communication Technologies (ICTs) (Noorani, Picot, 2001). This type of care was boosted by the global health crisis of the COVID-19 pandemic, becoming promising for cost reduction and optimization of access to health services (Garfan et al., 2021). Thus, it enables the provision of health care in remote areas, regions with a shortage of professionals, without the need for a robust care infrastructure. In the context of post-stroke rehabilitation, telerehabilitation can overcome significant barriers, such as dependence on caregivers, financial problems, lack of regional medical resources, and transportation challenges, by making rehabilitation feasible for stroke survivors in adverse settings (Chumbler et al., 2012; Sarfo et al., 2018).

In the context of telerehabilitation, multidisciplinary intervention is also a fundamental factor in ensuring the quality of treatment in stroke services (Clarke; Forster, 2015). The multidisciplinary team for post-stroke treatment is composed of multiple health professionals, many of whom include an occupational therapist. Occupational Therapy is a field of knowledge and profession focused on occupation and aimed at strengthening support for the individual to achieve performance, aiming at the acquisition of "new patterns that meet their personal needs and desires" (Kielhofner, 2006, p. 66). In the context of physical rehabilitation and post-stroke treatment, this objective translates into the recovery of skills necessary for performance in ADLs and IADLs.

It is estimated that 22.6% of healthcare costs are allocated to musculoskeletal dysfunctions (Briggs et al., 2018), indicating the significant demand for rehabilitation services. However, there is a mismatch between supply and demand, resulting in extensive waiting lists in healthcare services (Meneses; Silva; Silva, 2020). From this perspective, the importance of specific strategies for managing, regulating, and optimizing waiting lists is evident, since early intervention for individuals affected by stroke is essential for a good prognosis (Zeiler, 2019). It is also important to consider that the post-stroke recovery process is multifactorial, with genetic, pathophysiological, environmental, and therapeutic factors determining the overall course of recovery (Włodarczyk et al., 2021).

There is still no formal structure for telehealth, so access to this type of service can occur in various ways (Galea, 2019), and studies on its applicability are needed. It is also important to consider that access to specialized care is still a major bottleneck; the average waiting time for care in universal systems can exceed 10 months (Edwards; Hensher, 1998; Katz et al., 2020). Given the increasing use of telehealth by occupational therapists in the Brazilian Unified Health System (SUS) and the incorporation of digital technologies in the health field, it presents a potentially effective strategy to optimize the efficiency of rehabilitation services (Eroğlu et al., 2020).

RESEARCH PLAN

HYPOTHESES

This study will examine the effect of using telerehabilitation as an occupational therapy intervention strategy for stroke patients, as clinically indicated, who are awaiting in-person care from this same professional category, whether outpatient or inpatient, at the Institute of Physical Medicine and Rehabilitation of the Hospital das Clínicas of the Faculty of Medicine of the University of São Paulo (IMREA HCFMUSP).

GENERAL OBJECTIVE

To determine the effects of Occupational Therapy services provided through telerehabilitation for the population with sequelae from CVA who are awaiting outpatient or inpatient inpatient care.

SPECIFIC OBJECTIVES

To establish the occupational performance of participants through the application of specific scales, using occupational therapy intervention via telerehabilitation;

To demonstrate and analyze the challenges and limitations during the application of telerehabilitation services to stroke patients participating in the study;

To identify telerehabilitation as a strategy for optimizing care and access to public rehabilitation services.

METHODS

In order to answer the research objectives, a randomized controlled trial study was chosen. This is a pilot study that will be developed through the proposal of telerehabilitation sessions for patients on a waiting list, with a medical prescription, for Occupational Therapy care at the IMREA FMUSP, linked to the Lucy Montoro Rehabilitation Network.

A convenience sample will be used (20 users, divided equally into two groups), considering that patients awaiting care will be subject to the research eligibility criteria and will be selected in descending order (selected in reverse chronological order from the waiting list) to allow sufficient time for the intervention. If a study participant, regardless of the group to which they belong, is called to begin in-person Occupational Therapy care, a final assessment will be applied, concluding the follow-up.

Data collection for initial and final assessments will be conducted by an independent researcher, not involved in the study, allowing for a single-blind study. Participants will be divided into two groups using randomization: intervention and control. The first group (intervention) will participate in one 45-minute session per week for eight weeks. During this

RESEARCH PLAN

time, participants will receive guidance and perform therapeutic activities to improve occupational performance. The second group (control) will remain on the waiting list, without a specific intervention, as they were already waiting for care. Both groups will undergo initial assessments in the first session and final assessments in the last session. Jerry Dallal's randomization tool (Dallal, 2020) will be used to classify participants into the first and second groups. Allocation, at a 1:1 ratio, will be conducted by an independent researcher who will not participate in data collection or statistical analysis. The concealed allocation will be implemented using sequentially numbered, opaque, and sealed envelopes. A blind evaluator will open the sealed envelopes after the Informed Consent Form (ICF) has been signed and will conduct the evaluation of the participant in person. Those participants selected by lottery, belonging to the intervention group, will be given a schedule with the dates and topics that will be addressed in each session. Participants in the control group will sign the ICF and complete the structured questionnaire and rating scales.

The following research protocols will be used as data collection instruments: Katz Scale (Lino et al., 2008) for assessing ADLs; Scale of Instrumental Activities of Daily Living (Dos Santos; Júnior, 2008) for measuring performance in IADLs; and Motor Activity Log (MAL) for assessing hand motor function (Saliba et al., 2011). The study will be conducted according to the Consolidated Standards of Reporting Trials (CONSORT) and the Standard Protocol Items: Recommendations for Interventional Trials (SPIRIT).

Participants will also be given a structured sociodemographic questionnaire, developed by the researcher, to collect demographic data, including age, sex, educational level, and other data. Similarly, clinical data will be collected, such as the duration of hemiplegia, laterality of the affected body, etiology, hand preference, risk factors, and motor stages according to the Brunnstrom model (Naghdi, 2010). The questionnaire will be administered by the independent researcher at the time of randomization.

Thus, based on the research instruments presented, the research will be structured in five stages: i) recruitment of eligible patients; ii) randomization; iii) application of scales and structured questionnaire (intervention and control groups); iv) occupational therapy intervention via telerehabilitation (intervention group); v) final evaluation (intervention and control groups); vi) data processing and analysis.

Inclusion criteria

Adult patients, clinically stable, regardless of sex, race/color, aged 18 years or older, who present with sequelae of stroke, regardless of the Rankin scale score (Rankin, 1957), on a waiting list and according to medical indication for Occupational Therapy care at IMREA HCFMUSP. Individuals must also have access to a computer, tablet, and smartphone with an internet connection that allows for video calls, understand the Portuguese language, and have the assistance of a caregiver during therapy sessions, if necessary.

Exclusion criteria

RESEARCH PLAN

Clinically unstable patients, such as frail elderly individuals with decompensated chronic diseases and high-risk pregnant women **and individuals** under 18 years of age who are not on a waiting list for Occupational Therapy at IMREA HCFMUSP, in accordance with medical indication. Individuals who do not have access to a computer, tablet, or smartphone with an internet connection, and who do not have a caregiver when needed during therapy sessions, will also be excluded.

RISK ANALYSIS

The research presents a low risk of harm to participants, as it involves remote guidance, not exposing the user to any type of invasive procedure or risk associated with travel for appointments. However, the nature of stroke can result in significant variations in the cognitive and physical abilities of patients, which may interfere with adherence to and development of therapeutic interventions through telerehabilitation. Regarding the proposal to conduct remote appointments via video call platforms, there is a risk that sessions may be compromised due to technical and connection problems at the time of the sessions, potentially leading to difficulties in understanding and hindering the visualization and interpretation of instructions, inhibiting or hindering participation. Interruption of remote appointments will occur due to health problems and personal issues of the patient that prevent their participation; recurring technical issues that prevent the patient from accessing sessions; lack of interest from the research participant in continuing treatment; as well as the start of in-person Occupational Therapy appointments. To minimize such risks, a set of measures and/or procedures will be taken to ensure the privacy, confidentiality, and security of participants and their information. These are: i) data collection through scales and the structured questionnaire will be carried out manually, and only the researchers involved in the research will have access; ii) data collected manually will be digitized and stored on institutional servers; iii) personal information of participants related to the information provided will not be part of the research records, including any information that could be used to establish, identify, or reveal the participant's identity, or any other data that may be requested by the participant will be discarded from the research records; iv) depending on the degree of difficulty the patient has in performing the activities through telerehabilitation, it will be necessary for them to have a family member or caregiver present during the session; v) the participant will have complete freedom not to participate or to withdraw their consent at any time, even after the conclusion of the research, without any penalty, and will have confidentiality and privacy. vi) Nevertheless, in the event of harm or distress, the researcher is committed to providing support and referring participants to the physician responsible for the patient, without any expenses for the participants.

BENEFITS

The benefit of this research to individuals diagnosed with stroke and to occupational therapists working in the rehabilitation field within the Brazilian Unified Health System (SUS) is direct. For patients, it represents a possible structuring of another healthcare pathway in the

RESEARCH PLAN

rehabilitation process. For professionals, the research is linked to expanding knowledge about the use of telehealth for rehabilitation interventions within the SUS. The benefits for other professional categories are indirect, through support for research aimed at developing and improving the skills necessary for providing virtual healthcare services.

DATA ANALYSIS

The data collected through assessments and the structured questionnaire will be organized and classified according to their variables in digital spreadsheets. Subsequently, this data will be stratified using STATA software for statistical analysis. The effects of telehealth and the occupational performance of the participants will be determined by comparing the means between the intervention and control groups, as observed in the study assessments. The analysis method will be defined as either the Student's t-test or the Wilcoxon test, depending on whether the data are parametric or non-parametric, after normality tests using Shapiro-Wilk and evaluation of histograms or q-q plots. The other objectives will be analyzed descriptively. The information obtained will be correlated with the bibliographic material collected, aiming to integrate the results and draw conclusions about the use of telerehabilitation by occupational therapists.

FINANCIAL RESOURCES

The research will not receive direct public or private funding. Expenses related to equipment, personnel, materials and supplies, among other costs necessary for the project, are already integrated into the routine of the health service. Thus, these costs will not represent an additional burden on the institution's operation.

TIMELINE

The planned research schedule will be executed, as per Table 1, if the project is approved by the CEP/CONEP System. The same will occur within a period of 11 months.

Stage Identification	Month										
	0 1	0 2	0 3	0 4	0 5	0 6	0 7	0 8	0 9	1 0	1 1
Field research - participant recruitment and randomization	X	X									
Field research - initial application of questionnaires and scales (group, intervention, and control)	X	X									
Field research - occupational therapy intervention via telerehabilitation (intervention group)		X	X	X	X						
Field research - application of final assessments (group, intervention, and control)				X	X						
Bibliographic research					X	X					

RESEARCH PLAN

Data analysis					X	X	X				
Research report							X	X	X		
Development of Residency Completion Project						X	X	X	X	X	

PROCEDURES AFTER COMPLETING THE RESEARCH

Following the conclusion of the research, the researchers commit to the public dissemination of the results, whether favorable or unfavorable, either through the development of a scientific article or presentations at academic events such as congresses, symposia, and others. This commitment relates to the dedication to scientific dissemination so that the research has a significant impact on the advancement of knowledge and the improvement of healthcare for patients with stroke sequelae.

REFERENCES

1. BRASIL. Conselho Federal de Fisioterapia e Terapia Ocupacional. Dispõe sobre teleconsulta, telemonitoramento e teleconsultoria [Internet]. COFFITO. Resolução nº 516, de 20 de content/uploads/2020/03/Resolucao516_2020.pdf
2. BRIGGS, Andrew M. et al. Reducing the global burden of musculoskeletal conditions. **Bulletin of the World Health Organization**, v. 96, n. 5, p. 366, 2018.
3. CASON, Jana. Telehealth opportunities in occupational therapy through the Affordable Care Act. **The American Journal of Occupational Therapy**, v. 66, n. 2, p. 131-136, 2012.
4. CHAN, An-Wen et al. SPIRIT 2013 Statement: defining standard protocol items for clinical trials. **Revista Panamericana de Salud Pública**, v.38, p. 506-514, 2015.
5. CLARKE, David J.; FORSTER, Anne. Improving post-stroke recovery: the role of the multidisciplinary health care team. **Journal of multidisciplinary healthcare**, p. 433-442, 2015.
6. DALLAL, G. E. Randomization Plans: Randomizing Subjects to a Single Treatment, 2020 (acesso 19 novembro 2024), <http://www.jerrydallal.com/random/assign.htm>.
7. DE OLIVEIRA, P. et al. Terapia por caixa de espelho e autonomia no autocuidado após acidente vascular cerebral: programa de intervenção. **Revista de Enfermagem Referência**, v. 4, n. 17, p. 95-105, 2018.

RESEARCH PLAN

8. DOS REIS, M. F.; CHAOUBAH, A.. Gastos do Sistema Único de Saúde e do Regime Geral de Previdência Social com o acidente vascular cerebral: Brasil, 2020. **Revista Eletrônica Acervo Saúde**, v. 24, n. 2, p. e14884-e14884, 2024.

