- 22) Do you have a caregiver or family member who assists with daily tasks? ()Yes ()No
- 23) Do you have a family history of stroke? ()Yes ()No

III - Education

- 24) Level of education: ()Illiterate ()Can read and write ()Elementary education ()High School ()Higher education ()Postgraduate studies

IV - Income

- 25) Do you have health insurance? ()Yes ()No
- 26) Income: ()less than minimum wage ()up to one minimum wage ()between 2 and 3 minimum wages ()4 to 5 minimum wages ()more than 6 minimum wages

V - Assistive Technology

- 27) Assistive technology: ()Wheelchair ()Walker ()Single-point cane ()Forearm crutch ()Shower chair ()Hearing aid ()Orthosis ()Other - Specify
- 28) Do you wear corrective lenses?: ()Yes ()No
- 29) Uses dentures: ()Yes ()No

VI - Health condition

- 30) Injury time: _____
- 31) Date of injury: _____

RESEARCH PLAN

32) Type of stroke: ()Ischemic ()Hemorrhagic
 33) Medications: ()Antihypertensive ()Antiplatelet agent ()Anti-inflammatory ()Antidepressant ()Antipsychotic ()Antidiabetic ()Anticonvulsant ()Sedative ()Analgesic ()Diuretic ()Other - Specify
 34) Associated diseases: ()Rheumatological ()Genitourinary ()Endocrine ()Gastrointestinal ()Cardiovascular ()Respiratory ()Other - Specify
 35) Current pain?: ()Yes ()No
 36) Pain location: _____
 37) Presence of sensory alterations: ()Yes ()No
 38) Location of sensory alteration: _____
 39) Currently smokes: ()Yes ()No
 40) Former smoker: ()Yes ()No
 41) Consumes alcoholic beverages: ()Yes ()No

5. Schedule of appointments (intervention group)

Service Number	Intervention Focus	Duration (min)	Description	Responsible
1	Initial assessment (in person)	60	Application of the structured questionnaire, and the scales Instrumental Activities of Daily Living Scale, Katz Scale, and Motor Activity Log.	Independent researcher
2	Guidelines on the importance of mobility/positioning/posture of the body and the affected upper limb (telehabilitation)	45	To provide guidance on the importance of body and affected upper limb mobility/positioning/posture for: prevention and treatment of muscle contractures; improvement of joint mobility; improvement of blood circulation; reduction of spasticity; prevention of secondary injuries; improvement of neuromuscular function and coordination; prevention of muscle atrophy.	Researcher responsible

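### Time since stroke is unrestricted and recorded, but used in neither allocation nor analysis; with 20 patients a chance imbalance could shift the estimate by about 0.2 to 0.6 SD under stated assumptions

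*Combined protocol and SAP*

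**What the plan says.** **Eligibility.** The inclusion criteria admit adults "who present with sequelae of stroke, regardless of the Rankin scale score", on the waiting list and with a medical indication. Neither the inclusion nor the exclusion criteria limit time since stroke. METHODS adds that patients are "selected in reverse chronological order from the waiting list".

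**Allocation.** METHODS plans a convenience sample of 20, ten per arm, assigned with a web randomization tool: "Allocation, at a 1:1 ratio, will be conducted by an independent researcher who will not participate in data collection or statistical analysis". On concealment it says: "The concealed allocation will be implemented using sequentially numbered, opaque, and sealed envelopes". No stratification, blocking or minimization is described. Controls keep waiting and receive no study treatment.

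**Data.** METHODS lists duration of hemiplegia among the clinical variables. Appendix 4, section VI, asks for "30) Injury time" and, as item 31, for the date of injury.

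**Analysis.** DATA ANALYSIS compares group means by t-test or Wilcoxon test, chosen after a normality check. No covariate is named, neither the baseline score nor time since stroke.

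**The concern.** The general objective is to determine the effects of telerehabilitation, and the only protection against natural recovery is that the arms are alike. If patients early after stroke improve on the Katz, IADL or MAL scales over about two months without therapy, and late patients improve less, an arm with more early patients will look better whatever the treatment does. With ten per arm, similarity in time since stroke is left to chance, and the planned test does not use the variable that would reveal and correct an imbalance. The baseline score need not stand in for it: on the same assumption, two patients with equal scores but different times since stroke have different expected courses.

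**Working it through.** **Plan's own figure.** The sample size of 20 comes with no alpha, power, effect size or SD, so there is nothing to reproduce.

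**Inputs from the documents.** N = 20, n = 10 per arm, no stratification described, unadjusted comparison of means.

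**Assumptions not in the documents.** K = 4 to 10 of the 20 are early after stroke. Early patients gain δ = 0.5 to 1.5 SD more without therapy, where SD is that of the change score within early or late patients. Two-sided alpha is 0.05.

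**1. Chance of imbalance.** The number X of early patients in one arm is hypergeometric (20, K, 10), and the arms differ by |2X − K| early patients. With C(20,10) = 184,756, the probability of a difference of 4 or more is:

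- K = 4: 2 × 8,008 / 184,756 = 8.7%
- K = 6: 2 × 13,013 / 184,756 = 14.1%
- K = 8: 2 × 15,686 / 184,756 = 17.0%
- K = 10: 2 × 16,526 / 184,756 = 17.9%

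These are two-sided. The chance of an imbalance favouring telerehabilitation is half: 4.3% to 8.9%. For time since stroke as a continuous variable, the standardized difference between arms has SD √(2/10) = 0.447, so a difference of at least 0.5 has probability of about 26%.

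**2. Size of the shift.** Four extra early patients among ten shift the difference in means by (4/10) × δ, that is 0.2, 0.4 and 0.6 SD for δ = 0.5, 1.0 and 1.5.

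**3. Yardstick.** The standard error of a difference in means is √(2/10) = 0.447 SD. The shift is therefore 0.2/0.447 = 0.4 to 0.6/0.447 = 1.3 standard errors.

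**4. Effect on the test.** Simulation with no treatment effect, change = δ × early + N(0,1), K = 6, 8 and 10, and 40,000 trials per scenario. Ranges run over K. "Given imbalance" means 4 or more extra early patients in the intervention arm.

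| δ | Type I error, all allocations | Mean shift given imbalance | False result favouring telerehabilitation given imbalance (nominal 2.5%) | SD of estimate, unadjusted | SD of estimate, adjusted |
|---|---|---|---|---|---|
| 0.5 | 5.0–5.2% | 0.21–0.22 | 5.9–7.1% | 0.46 | 0.46 |
| 1.0 | 4.7–5.0% | 0.41–0.43 | 9.7–10.8% | 0.50 | 0.46 |
| 1.5 | 4.8–5.2% | 0.63–0.64 | 14.8–15.8% | 0.55–0.56 | 0.46 |

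Adjusting for early/late brings the conditional shift to within about 0.01 SD of zero and the conditional two-sided rejection rate to 4.3–5.6%. At δ = 0.5 it gains no precision; the gain appears at 1.0 and 1.5.

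**5. Stratified allocation.** With an equal split within each stratum the shift is zero by design and the SD of the estimate is about 0.45. An unadjusted t-test is then conservative: type I error falls to between 4.5% and 1.5%.

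The simulation did not include a baseline score, so it says nothing about the further gain from adjusting for one.

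**The case against.** The strongest reply is that chance imbalance under concealed randomization is part of the sampling error that the test already allows for. That stands. A reader might infer that the design is biased or that its false-positive rate is inflated, and neither is so: over all allocations the error rate is 4.7–5.2%. What remains is conditional: once an unlucky draw has happened, the unadjusted estimate is off and the data to correct it lie unused.

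A reader might also infer that newest-first selection makes matters worse by bringing in recent strokes. The documents do not support this. The waiting-list date is not the stroke date. If the two are related, newest-first selection makes the sample more uniform; if not, the order is irrelevant.

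Nor does the introduction establish the premise. It says that "early intervention for individuals affected by stroke is essential for a good prognosis", which concerns the timing of treatment, and its list of what drives recovery does not name time since stroke. The support is indirect, and the size of natural recovery has to be assumed.

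Two further points carry some weight. The study calls itself a pilot, which lowers the stakes, although it still tests for an effect. Duration of hemiplegia is collected and CONSORT reporting is promised, so an imbalance could be shown; showing it does not remove it from the estimate. Severity may matter as much, since any Rankin score is eligible. That is a reason to put the baseline score in the model as well, not to leave time since stroke out.

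**Conclusion.** The point holds as one of conditional bias and lost precision. The arms differ by 4 or more early patients with probability 9% to 18% if 4 to 10 of the 20 are early. Such a draw shifts the estimate by about 0.2 to 0.6 SD if early patients gain 0.5 to 1.5 SD more untreated. At the low end this is less than half a standard error and adjustment gains little; at the high end it exceeds one standard error. The shift can equally mimic or hide an effect. Both ranges are assumptions. The absence of a time limit, a stratification factor and a covariate is plain from the documents. The change is worth making because the variable is already collected.

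**What to change.** Before any outcome is seen, replace the unadjusted two-group test in DATA ANALYSIS with a linear model (ANCOVA), for each scale, of the final score on group, baseline score and time since stroke. Take time since stroke from item 30, or use one early/late cut-off, and fix that choice in advance. If residuals are clearly non-normal, use a rank-based or permutation version of the same model.

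**Cost.** One degree of freedom for time since stroke and one for the baseline score, so residual degrees of freedom go from 20 − 2 = 18 to 20 − 4 = 16. A covariate cannot be added to a t-test or Wilcoxon test, so the method itself changes. No new data, visit or staff are needed.

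**Optional: stratified envelopes.** These are workable only if the stroke date is available before the envelope is opened. The documents do not say that the referral carries it, and the stages in METHODS put randomization before the questionnaire. If envelopes are stratified, the stratum must also be in the model, because an unadjusted test would be conservative. Small blocks within strata of about ten patients would also make late allocations easier to guess. With 20 patients, one stratification factor is the practical limit.
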